## **STATEMENT OF COMPLIANCE**

The study will be conducted in accordance with the International Conference on Harmonisation guidelines for Good Clinical Practice (ICH E6), the Code of Federal Regulations on the Protection of Human Subjects (45 CFR Part 46), and the NIDCR Clinical Terms of Award. All personnel involved in the conduct of this study have completed human subjects protection training.

## LIST OF ABBREVIATIONS

*{Please add all disease or study-specific abbreviations/acronyms in this section. Modify this list as needed for your particular study and remove abbreviations that are not used in the document.}*

AE	Adverse Event/Adverse Experience
CFR	Code of Federal Regulations
CHCO	Children's Hospital Colorado
CHOP	Children's Hospital of Philadelphia
CRF	Case Report Form
DCC	Data Coordinating Center
DSMO	Data and Safety Monitoring Officer
EOE	Eosinophilic Esophagitis
EREFs	Endoscopic Reference System
EST	Esophageal String Test
GCP	Good Clinical Practice
HIPAA	Health Insurance Portability and Accountability Act
ICF	Informed Consent Form
ICH	International Conference on Harmonisation
IRB	Institutional Review Board
ISM	Independent Safety Monitor
MOP	Manual of Procedures
N	Number (typically refers to participants)
NIH	National Institutes of Health
OHRP	Office for Human Research Protections
OHSR	Office of Human Subjects Research
PEESS	Pediatric Eosinophilic Esophagitis Symptom Scores
PI	Principal Investigator
QA	Quality Assurance
QC	Quality Control
SAE	Serious Adverse Event/Serious Adverse Experience
SOP	Standard Operating Procedure
US	United States

Title:	Use of Esophageal String Test to understand symptoms, inflammation and function in eosinophilic esophagitis
Overview:	Presently, the only method available to monitor disease activity in Eosinophilic Esophagitis is endoscopy with pathological review of biopsies. The overall goal of this study is to determine the ability of the Esophageal String Test (EST), a minimally invasive capsule based technology, to measure disease activity in children with EoE.
Objectives:	
Primary Aim: Do eosinophil proteins captured by the EST correlate with symptoms related to pediatric EoE?
 
Secondary Aim 1: Do eosinophil proteins captured by the EST correlate with the markers of EoE pathogenesis?
 
Secondary Aim 2: Do eosinophil proteins captured by the EST correlate with a measure of esophageal function?

Population:	40 subjects: males and females, ages 7-18 years old undergoing upper endoscopy for monitoring of EoE or for symptoms of esophageal dysfunction concerning for EoE
Study Sites:	
Lead Site: Children's Hospital of Colorado
 
Recruitment Site: Children's Hospital of Philadelphia
 
Clinical Laboratory: University of Illinois, Chicago

Site Principal Investigators	
[name]; University of Illinois, Chicago
 
[name]; Children's Hospital of Philadelphia

Study Duration:	2 years
Subject Participation Duration:	1 month
Estimated Time to Complete Enrollment:	18 months

## 1 INTRODUCTION: BACKGROUND INFORMATION AND SCIENTIFIC RATIONALE

### 1.1 Background Information

Eosinophilic Esophagitis (EoE) is a chronic disease characterized by symptoms related to esophageal dysfunction and large numbers of eosinophils in the lining of the esophagus (1). An endoscopy is required to make the diagnosis, because a biopsy of the esophageal tissue needs to be examined under the microscope. Eosinophils contain a number of proteins that likely participate in their function. Eosinophil peroxidase, major basic protein, eosinophil cationic protein and eosinophil derived neurotoxin are four of the major proteins that are associated with the eosinophil's function.

The EST is a capsule filled with a 90cm nylon string. A trailing end of the string protrudes from one end of the capsule. This end is taped to the cheek and the capsule is swallowed. As the capsule travels to the small intestine, the string inside the capsule is dislodged, leaving a string that goes from the cheek to the small intestine. The capsule dislodges from the string and the string is left in place, in the mouth, esophagus, stomach and small intestine for an hour. During this time, the string rubs against the inside of the esophagus and collects eosinophil proteins. After one hour, the string is removed through the mouth and placed in preservative to save the eosinophil proteins. The fluid extracted from the string is analyzed in the laboratory for eosinophil proteins. In a previous study, we showed that the eosinophil proteins captured by the string correlated with the number of eosinophils and amount of eosinophil proteins in the tissue biopsy (2). In this proposal, we will measure eosinophil proteins contained in the EST and correlate that with esophageal symptoms, inflammatory proteins and function.

### 1.2 Rationale

Procurement of mucosal biopsies during sedated endoscopy is the only method to determine whether a child may have eosinophilic esophagitis (EoE). Counting esophageal eosinophils in the squamous epithelium remains key to establishing the diagnosis. To date, no blood, stool, breath or other peripheral sampling of eosinophil related biomarkers has been shown to correlate with mucosal eosinophilia in esophageal biopsies, thus leaving patients and families with the only option of undergoing this invasive, costly and time consuming procedure. Sedated upper endoscopy with biopsy is a safe procedure, but alternative methods that limit or eliminate exposure to anesthetic agents and address other problematic features are needed to obtain diagnostic samples. Although eosinophils are easy to count, variability exists with respect to reporting, and better biomarkers must be determined. In this regard, we, and others showed that effluents obtained from the esophageal lumen are reflective of esophageal eosinophilia. Katzka et al determined that the esophageal sponge is able to harvest mucosal scrapings to measure eosinophils (10). This approach is not suitable for children because of its size and tolerability. Our work documents that the Esophageal String Test (EST) can detect luminal biomarkers that reflect esophageal eosinophilic infiltration (2). This capsule based technology is well tolerated by children ages 7 years and up, and fluid adherent to the string has been shown to contain eosinophil granule proteins that correlate with esophageal eosinophilia and amounts of these proteins in biopsies.

The overall goal of this study is to discover a less invasive fashion to make the EoE diagnosis and assess disease activity in children. Here, we will determine whether eosinophil granule proteins captured by the EST correlate with: a) EoE symptoms, b) EoE histopathological scores and inflammatory proteins and c) a new functional biometric, distensibility. In this proposal, we hypothesize that luminal eosinophilic granule proteins will correlate with symptoms, inflammatory proteins and distensibility.

### **1.2.1 Potential Risks**

The study involves *greater than minimal risk with no prospect of direct benefit*.

Since the patient will be undergoing endoscopy/colonoscopy for diagnostic purposes regardless of this study, the benefits to the subject and society outweigh the minimal risks associated with the additional biopsies. The procedure will present the subject with an experience that is the same as that expected in the standard of care. Risks associated with endoscopy and colonoscopy with biopsy include perforation, hemorrhage and the risks of conscious sedation.

While upper endoscopy with esophageal biopsy is greater than minimal risk, only those patients consenting for and receiving upper endoscopy with biopsy for evaluation of GI symptoms as recommended by their primary clinician as part of routine care will be approached for study. The additional biopsies for research purposes are therefore of minimal risk beyond routine clinical care.

The safety of multiple biopsies is supported by studies on adult patients with Barrett's esophagus that have shown that multiple esophageal biopsies (as many as 35 to 120 esophageal biopsies in an individual patient) do not produce esophageal perforation or bleeding when performed by an experienced team of physicians, nurses, and technicians (48). In addition, a recent NIH study demonstrated that obtaining multiple mucosal biopsies for research purposes during elective endoscopy is well tolerated and appears to have no more than minimal risk without appreciably increasing the risk of otherwise routine endoscopy (49). Importantly, there was no statistically significant association between the number of biopsies, type of procedure, anatomic location of research biopsies, endoscopist, or the use of nonsteroidal anti-inflammatory drugs and the risk of complications.

A recent review of the incidence of perforation and other severe complications associated with upper endoscopy was performed at Children's Hospital Colorado. In a 42 month period of study there were 8 documented episodes of perforation out of 8130 endoscopic procedures. In all 8 cases the patient had undergone an interventional endoscopic procedure (4 esophageal dilations, 2 gastrojejunostomy placements, 1 foreign body removal and 1 polypectomy). None of the perforations was the result of esophageal mucosal biopsies performed during diagnostic EGD. The incidence of perforation associated with pediatric gastrointestinal endoscopy performed by pediatric gastroenterologists is low. In the 3.5 year period of study, 5683 diagnostic EGD's were performed here at CHCO. There were no documented complications resulting from esophageal mucosal biopsies, including bleeding requiring blood transfusion, tamponade, or cauterization. There were 5 diagnostic EGD's (0.09%) which presented after endoscopy with symptoms concerning for upper GI bleeding (hematemesis/coffee ground emesis), 4 of which were referred to the ED, but none of whom required blood transfusion or additional intervention.

EndoFLIP has been shown to be safe in adults and children without increased risk of bleeding or perforation. Parameters can be set to limit the degree of inflation permitted. EndoFLIP will add approximately an additional 10 minutes of sedation time to overall procedure.

Allergic reaction to the gelatin in the capsule is the only associated risk with the EST. The EnteroTracker device contains a small metal ball to weigh down the string. Subjects should tell their providers they have swallowed the ball and xray should be ordered prior to undergoing an MRI after completed the study. The small ball should pass within 24-48 hours in healthy individuals.

There are no differences in the risks to the experimental group (patients with eosinophilic GI diseases) and the control groups (other inflammatory diseases and those with normal

mucosae). No treatments will be administered. Specific procedures are in place to protect the patient including using the smallest biopsy forceps and smallest capsule indicated as well as automatic stoppage of EndoFLIP insufflation at set intrabag pressures and volumes. Risks are minimized by qualified investigators closely monitoring subjects, and appropriate use of inclusion/exclusion criteria.

Patient confidentiality will be maintained. Violation of privacy and loss of confidentiality are both risks to which research participants are exposed. The possibility of these risks increases when protected health information is collected

**Describe plan to minimize risk.** We will minimize risk by excluding those patients at potential or theoretical increased risk of bleeding or perforation from esophageal mucosal biopsies (See exclusion criteria) and with the below mentioned stopping rules. EndoFLIP will only be performed by endoscopists trained in these tools to avoid unnecessary prolongation of procedure and anesthesia time.

**Stopping Rules.** A subject will be able to discontinue the study any time after giving consent up until time of procedure. Subjects will need to be re-consented if ever undergoing repeat procedure. If, during the procedure, there is real or anticipated complication on the part of the physician(s) related to anesthesia or procedure, the research procedure will be stopped. Protocol stopping criteria include any grade 3 complication.

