### **4.1 Subject Inclusion Criteria**

In order to be eligible to participate in this study, an individual must meet all of the following criteria:

- Provide signed and dated informed consent form.
- Willing to comply with all study procedures and be available for the duration of the study.
- Male or female, aged 7 to 18 years old, inclusive
- Undergoing upper Endoscopy with biopsy for clinical care at CHCO or CHOP
- Current or historical diagnosis of EoE, or suspected of having EoE

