### **4.2 Subject Exclusion Criteria**

An individual who meets any of the following criteria will be excluded from participation in this study:

- Known connective tissue disease, other eosinophilic disorders
- Past history of caustic ingestion, esophageal surgery or other esophageal injury
- Known inflammatory bowel disease or esophageal motility disease (achalasia)
- Unwilling or unable to swallow the EST
- Oral or intravenous steroids in the preceding 60 days (not including swallowed topical fluticasone, budesonide, etc)
- Pregnancy
- Participation in a clinical study that may interfere with participation in this study

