## 5 STUDY SCHEDULE

**Screening/ Consenting** (Day -7 to 0) When children are scheduled to undergo an endoscopy, research assistants will review the child's information for basic inclusion/exclusion criteria. They will then contact the family to discuss the study. The CRC will email or fax the consent form to families in order to provide ample opportunity to review the consent form. Families who agree to the study will be scheduled to consent for the study up to one week prior to the scheduled EGD or on the day of the EGD before the EGD scheduled time.

**Baseline Visit** (Day 0): All procedures can be completed in one day if the subject agrees. If so, the baseline visit will be the only visit for the subject. The baseline visit should be completed as follows:

- Obtain Informed Consent
- Obtain Subject Medical History and complete Study Inclusion/Exclusion criteria
- Obtain subject's height
- Administer the PEES
- Administer EST device (subjects are allowed up to 8 ounces of water to assist in the swallowing of the EST)
- After 1 hour, remove the EST and assess for adverse events
- Accompany subject to procedure center for check in
- Obtain biopsies during EGD
- Perform EndoFLIP during EGD

**Follow Up Visit** (Day 1-3): Research Coordinators should contact subjects between 1-3 days after procedures are completed and assess for any adverse events.

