**Functional Luminal Imaging Probe (FLIP):** After endoscopic visualization, the FLIP, a 16 cm probe (Crospon) will be placed transorally and positioned 3 cm distal to the lower esophageal sphincter. Esophageal cross sectional areas and intrabag pressure will be measured during stepwise distensions beginning with 5 mL and increasing to a maximum of 70 mL or intrabag pressure of 50mmHg is achieved, whichever comes first. To prevent unintended dilation of a stiff esophagus, infusion will stop and alarm message will sound if intrabag pressure exceeds 60 mm Hg. Raw data will be exported to EndoFLIP Analytics and will be filtered to remove measurements during esophageal contractions and vascular and respiratory artifacts. A polynomial regression method to identify pressure to cross sectional area relationships will be used to determine outcomes, narrowest cross sectional area, and distensibility plateau. FLIP is FDA-approved without age restriction and its use has been approved by our IRBs previously. Primary results will be reported as distensibility plateau (mm).

**EST and biopsy samples:** The EST will be placed in a labeled tube and frozen until analysis as below. Four mucosal biopsies will be obtained from the distal esophagus for protein (3 biopsies) and histological (1 biopsy) analysis. Samples for protein analysis will be snap frozen for batch processing and assessment. Samples for histological analysis will be paraffin embedded and cut into 5 $\mu$ M sections for batch staining.

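### Section 1.2.1 says patients at raised bleeding risk are excluded and refers to the exclusion criteria, but no criterion in Section 4.1 or 4.2 covers bleeding

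*Combined protocol and SAP*

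**What the plan says.** Section 1.2.1 (Potential Risks) lists hemorrhage among the risks of endoscopy with biopsy. Its plan to minimize risk commits to "excluding those patients at potential or theoretical increased risk of bleeding or perforation from esophageal mucosal biopsies (See exclusion criteria". The same section also counts proper use of the eligibility criteria among the ways risk is kept down.

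Section 4.2 lists seven exclusions. The two that bear most clearly on biopsy risk are "Known connective tissue disease, other eosinophilic disorders" and "Past history of caustic ingestion, esophageal surgery or other esophageal injury". Section 4.1 lists five inclusion criteria, one of which is "Undergoing upper Endoscopy with biopsy for clinical care at CHCO or CHOP".

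Section 5 says how the lists are used. At screening, research assistants review the child's "information for basic inclusion/exclusion criteria". At baseline, staff are to "Obtain Subject Medical History and complete Study Inclusion/Exclusion criteria".

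Section 6.1 sets the tissue collection: "Four mucosal biopsies will be obtained from the distal esophagus for protein (3 biopsies) and histological (1 biopsy) analysis".

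**The concern.** Section 1.2.1 sets a low threshold for exclusion, since a merely theoretical increase in risk is enough. It names bleeding before perforation and tells the reader where the safeguard sits. A reader who turns to that list finds nothing on bleeding tendency.

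This matters because the list, not the narrative risk section, is what staff are told to work through for each child. The protocol itself classes the study as above minimal risk with no direct benefit to the child. In that setting, a protection offered to an ethics board or a family should be one that staff can apply and an auditor can verify. What is at stake is subject safety and internal consistency. Nothing in the statistical analysis depends on it.

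**Working it through.** No arithmetic decides this point. The check sets the commitment beside each criterion, then looks for a bleeding exclusion placed elsewhere.

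**Commitment (Section 1.2.1):** exclude for raised risk of (a) bleeding or (b) perforation from esophageal biopsy.

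**Exclusion criteria (Section 4.2):**

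| Criterion | Perforation | Bleeding |
|---|---|---|
| 1. Connective tissue disease or other eosinophilic disorder | plausible, through tissue fragility | not named |
| 2. Caustic ingestion, esophageal surgery or injury | plausible | not named |
| 3. Inflammatory bowel disease or achalasia | not evident | not named |
| 4. Cannot or will not swallow the string | no | no |
| 5. Systemic steroids within 60 days | not evident | not named; the only drug exclusion |
| 6. Pregnancy | no | no |
| 7. Interfering clinical study | no | no |

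Section 4.2 gives no purpose for its bullets, so the entries marked plausible are a reading of the list and not a statement in it.

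**Inclusion criteria (Section 4.1):** consent, willingness to comply, age 7 to 18, clinically indicated endoscopy with biopsy, and known or suspected eosinophilic esophagitis. None concerns bleeding.

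**Count:** 0 of 7 exclusions and 0 of 5 inclusions name a bleeding disorder, low platelets, or anticoagulant or antiplatelet use. Those conditions are examples chosen for this check. Section 1.2.1 promises a risk category and lists no conditions. The count shows missing wording and does not measure risk.

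**Elsewhere:**
- Section 5 asks for a medical history and the criteria check. It names no platelet count, clotting test or medication check.
- Section 6.1 describes the biopsies without a bleeding precondition.
- Section 4.5.1 lets the investigator end participation, either for a medical condition that occurs or because a listed exclusion is met. The second ground cannot work for bleeding risk, because no such exclusion is listed.
- Section 7 covers events after the procedures.

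**Exposure:** up to 3 + 1 = 4 biopsies for study analysis per child. This is the planned number. Section 9.3.1 lets families choose which components they consent to and gives declining tissue procurement as an example.

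**Background rate:** Section 1.2.1 reports 5,683 diagnostic upper endoscopies at the lead site with no documented biopsy complication. Five (5/5,683 = 0.09%) later had symptoms suggesting upper gastrointestinal bleeding, and none needed transfusion or further intervention. No results are given for children with a bleeding disorder or on anticoagulants, so the rate for the children at issue is unknown.

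**The case against.** The strongest reply is that the gap is narrow and other protections surround it.

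- Every subject already has a clinician-recommended endoscopy with biopsy, so the study adds only the research biopsies. This stands. Routine clinical screening for bleeding probably applies too, but that is an assumption, because the protocol does not describe it.
- The stopping rules say that if, during the procedure, there is a "real or anticipated complication on the part of the physician(s) related to anesthesia or procedure, the research procedure will be stopped". This has real force. Research biopsies are taken during the procedure, so a physician who foresees bleeding can withhold them. The rule rests on physician judgement and acts after eligibility is settled, so it limits exposure without supplying the criterion.
- The medical history could reveal a bleeding tendency, and Section 1.2.1 is itself protocol text. This also stands. What is missing is a listed criterion to check the history against.
- The safety data are reassuring. Section 1.2.1 also cites a study that found no significant association of complications with the number of biopsies or with nonsteroidal anti-inflammatory drugs. Neither source, as described, covers bleeding disorders or anticoagulants.
- The eligibility form or the Manual of Procedures mentioned in Section 8 may fill the gap. Neither is among the documents, so this cannot be settled. Section 1.2.1 points to the exclusion criteria and not to that manual.

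A reader might also go too far the other way and infer that the promised safeguard is missing altogether. The documents do not support that, because Section 4.2 gives the perforation half reasonable support.

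**Conclusion.** The point holds for bleeding only. Section 1.2.1 promises an exclusion that the lists in Sections 4.1 and 4.2 do not carry, so a child with a known bleeding risk could pass the written check and be scheduled for up to four study biopsies.

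Two stronger inferences are not supported. One is that the protocol permits knowingly enrolling such a child; doing so would go against Section 1.2.1. The other is that subjects face a material excess of bleeding. The documents give neither the number of such children nor a complication rate for them, and the protections around the procedure keep practical exposure small.

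The conclusion assumes that the criteria as printed are complete and that no unseen form adds a bleeding item. It is a minor point of patient safety and a cheap improvement. It does not touch aims, endpoints, sample size or analysis.

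**What to change.** Add one bullet to Section 4.2 excluding subjects with known increased bleeding risk, for example a bleeding disorder, thrombocytopenia, or current anticoagulant or antiplatelet therapy. The investigators should set the drug list and any platelet threshold. Add the same item to the eligibility form so that it is checked at screening and baseline.

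The cost is a short amendment, a check of the form, and possibly a few children who become ineligible. Deleting the bleeding assurance from Section 1.2.1 would also remove the mismatch, but it would give up the protection, so adding the bullet is the better choice.
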